15.7. CIP Amendments

Amendments to the CIP may be initiated by Medtronic to address changes to the conduct of the study.

Amendments to the CIP, and associated documents, must be approved by Medtronic and submitted to the IRBs for approval prior to implementation except when necessary to eliminate an immediate or apparent immediate hazard to participating subjects.

15.8. Required Reports and Records

15.8.1. Investigator Records

Documentation for this study will be produced and maintained to ensure that a complete history of the study exists. Documents created for this study, including all versions of original documents, will be identifiable and appropriately stored to assure control and traceability of data related to this study.

The principal investigator is responsible for ensuring that all essential study documentation is retained and accessible for 2 years (or longer as local law or hospital administration requires) after the

investigation is terminated or completed. The retention period may be longer if required by Medtronic or regulatory requirements. Medtronic will be responsible for notifying sites of extensions to the 2-year minimum record retention requirements. The principal investigator will ensure that essential study documents are not destroyed until written permission has been obtained from Medtronic. Medtronic will be notified in writing of any transfer of study documentation.

15.8.2. Investigator Reports

The principal investigator is responsible for the preparation (review and signature) and submission to the sponsor of all case report forms, reportable adverse events, device deficiencies, deaths, and any deviations from the CIP. If any action is taken by an IRB with respect to this clinical study, copies of all pertinent documentation must be forwarded to Medtronic in a timely manner. Reports are subject to inspection and to the retention requirements as described in Section 15.8.1 for investigator records.

15.9. Publication and Use of Information

[Redacted]

[Redacted]

[Redacted]

[Redacted]

[Redacted]

[Redacted]

[Redacted text block]

[Redacted text block]

[Redacted text block]

15.10. Suspension or Early Termination

Early termination is the closure of a clinical study that occurs prior to meeting defined endpoints. This is possible for the whole study or a single center. Suspension is a temporary postponement of study activities related to enrollment. This is possible for the whole study or a single center.

Medtronic reserves the right to suspend or terminate the study or an individual study site at any time.

Possible reasons for considering study suspension or termination of the study include but are not limited to:

- Adverse events associated with the system or product under investigation which might endanger the safety or welfare of the subject
- Observed/suspected performance different from the product's design intent
- Decision by Medtronic

Possible reasons for clinical investigator or center termination or suspension include but are not limited to:

- Failure to obtain initial IRB approval or annual renewal of the study
- Persistent non-compliance to the clinical study CIP (e.g. failure to adhere to inclusion/exclusion criteria, failure to follow subjects per scheduled follow-ups)
- Lack of enrollment
- Noncompliance to regulations and the terms of the clinical trial agreement (e.g. failure to submit data in a timely manner, failure to follow-up on data queries and monitoring findings in a timely manner, etc.)
- IRB suspension of the center
- Fraud or fraudulent misconduct is discovered (as defined by local law and regulations)

[Redacted text block]

- Investigator request (e.g. no longer able to support the study)

16. References

4.1. Primary Objective

To characterize the minimum amplitude as a percentage of perception threshold that maintains SCS therapy satisfaction.

4.2. Secondary Objective

To characterize the minimum amplitude as a percentage of perception threshold that maintains overall pain relief.

4.3. Additional Objectives

[Redacted content]

4.4. Safety Objective

To characterize therapy and device related adverse events and device deficiencies.

5. Investigation Plan

5.1. Study Design

The purpose of this study is to characterize the effects of amplitude titration on subject satisfaction and pain relief with HD stimulation (90 μ s and 1000 Hz) in subjects with back and leg pain being treated by SCS.

This is a prospective, multi-center, single-blind post-market feasibility study. This study will be conducted in the United States at no less than 2 sites. Approximately 60 subjects will be enrolled to get 40 subjects to proceed beyond baseline visit. To reduce the possibility of atypical results from a site overly influencing the combined results, no more than 30 subjects will be enrolled at each site. Eligible subjects will receive four different programmed amplitude settings (80%, 60%, 40%, and 20% of perception threshold), each for approximately two weeks. Subjects will be blind to the different amplitude settings and will not be informed that the amplitude is being titrated down, beginning at 80% of perception threshold.

The eligibility criteria will be assessed at both screening visit and baseline visit.

Inclusion criteria – screening visit

To be included in this study, a patient must meet the following inclusion criteria:

1. 22 years of age or older
2. Implanted with a RestoreSensor system (for back and leg pain) for at least 1 month
3. Has a program with only 1 anode and 1 cathode with 90 μ s and 1000 Hz and the group that contains the program is used \geq 50% (compared to the percent use of the other groups, if present).
4. Willing and able to provide signed and dated informed consent
5. Capable of comprehending and consenting in English
6. Capable of getting into the supine and sitting positions for perception threshold testing

[Redacted content]

7. Willing and able to comply with all study procedures and visits
8. On stable (no change in dose, route, or frequency) prescribed pain medications for at least 4 weeks before enrollment and willing to maintain dose during the study

Exclusion criteria – screening visit

To be included in this study, a patient must not meet any of the following exclusion criteria:

1. Implanted with leads for peripheral nerve stimulation or an implantable intrathecal drug delivery system
2. Had a pain-related surgery in the previous 1 month of enrollment or the intent to undergo surgery during the period of the study
3. Implanted with quadripolar lead
4. Currently enrolled or planning to enroll in a potentially confounding clinical study during the course of the study (co-enrollment in concurrent studies is only allowed when documented pre-approval is obtained from the Medtronic study manager (or designee))
5. Pregnant or is of child-bearing potential and unwilling to use a medically acceptable form of birth control during the study
6. Has untreated major psychiatric comorbidity, as determined by the investigator, or designee
7. Has serious drug-related behavioral issues (e.g., alcohol dependency, substance abuse), as determined by the investigator, or designee
8. Has unresolved major issues of secondary gain (ie, secondary reason not to report improvement in health condition), as determined by the investigator, or designee

Inclusion criterion – baseline visit

To proceed on with the Baseline visit, the subject must meet the following inclusion criteria:

1. Has an average overall VAS pain score ≤ 4 based on the Baseline diary

Exclusion criteria – baseline visit

[figure not shown]
To proceed on with the Baseline visit, the subject must not meet any of the following exclusion criteria:

1. Has provided response to Baseline SSA as “Neutral”, “Somewhat unsatisfied”, or “Very unsatisfied” with the therapy
2. Completed less than 5 of the 7 days of the Baseline diary

The overall study duration, from first subject enrollment to last subject visit, is expected to last approximately 15 months. Each subject’s participation in the study is expected to last approximately 12 weeks from enrollment. The completion of the study is defined as the approval of the Final Study Report and closure of all sites.

A summary of the study design is illustrated in Figure 1.

Figure 1: Study Visit Diagram

5.2. Study Measures

5.2.1. Efficacy Measures

5.2.1.1. Satisfaction and Stimulation Assessment (SSA)

Subjects will be asked to indicate their satisfaction with the therapy and details pertaining to any stimulation sensations. The SSA will include questions such as the following:

- Overall how satisfied or unsatisfied are you with this therapy?
 - Very satisfied
 - Somewhat satisfied
 - Neutral
 - Somewhat unsatisfied
 - Very unsatisfied
- Specify reason for this response?
- Have you felt any stimulation sensations?
 - No
 - Yes, specify the following:
 - Occasional or Continuous
 - Pleasant or Unpleasant
 - Position when felt (lying on back, lying on front, lying on right, lying on left, mobile, reclining, upright, other)

5.2.1.2. Visual Analog Scale (VAS) in Pain Diary

Pain will be assessed using the VAS in a pain diary. The VAS is a 10-cm line, with “No pain” on left and “Worst pain imaginable” on the right.

Subjects will record their overall, back, and leg pain using a paper pain diary once a day for a 7-day period prior to the scheduled study visits. For the initial baseline pain diary, completed prior to the baseline visit, subjects are required to complete at least 5 of the 7 days to ensure diary compliance during the study.

For the scheduled follow-up visits, the subject will be reminded to complete the diary for a 7-day period prior to the scheduled follow-up visit and the last 3 days of the diary will be used for the assessment.

The pain diary questionnaire will consist of questions such as the following:

- Please rate your pain by making a vertical slash mark through the line that best describes your average overall pain during the last 24 hours. (Line with “No pain” on left and “Worst pain imaginable” on the right)
- Please rate your pain by making a vertical slash mark through the line that best describes your average back pain during the last 24 hours. (Line with “No pain” on left and “Worst pain imaginable” on the right)

- Please rate your pain by making a vertical slash mark through the line that best describes your average leg pain during the last 24 hours. (Line with “No pain” on left and “Worst pain imaginable” on the right)

[Redacted]

[Redacted]

[Redacted]

5.2.2. Safety measures

Safety will be evaluated by the collection of device deficiencies and adverse events related to the following:

- The implanted SCS system and accessories
- Spinal cord stimulation therapy

6. Determination of Sample Size

An estimated 60 subjects will be enrolled in order for at least 40 subjects to proceed beyond the Baseline visit. A sample size of 40 subjects is reasonable to characterize the distribution of the minimum amplitude as a percentage of perception threshold that maintains SCS therapy satisfaction, as well as to provide data for consideration of future studies.

[Redacted]

7. Statistical Methods

7.1. Study Subjects

7.1.1. Disposition of Subjects

Subject disposition will be summarized using a flow diagram. Reasons for subject discontinuations will be summarized.

7.1.2. Clinical Investigation Plan (CIP) Deviations

All CIP deviations will be summarized by type of deviations. Details of CIP deviations that affect scientific integrity or patient safety may be presented.

7.1.3. Analysis Sets

Treated Analysis Set

Treated analysis set will include subjects who proceed beyond the baseline visit and receive at least one programmed amplitude setting.

Baseline Analysis set

Baseline analysis set will include subjects who met inclusion and exclusion criteria at both screening and baseline visits. These are the subjects who responded to HD stimulation, which is defined as having an average overall pain VAS ≤ 4 at baseline. The baseline characteristics will be summarized for one of the additional objectives.

Safety Analysis set

All subjects will be included in the safety analysis set.

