8.2. Subject Enrollment

Subjects are considered enrolled at the time the study-specific Informed Consent Form (ICF) is signed. Each subject must meet all the inclusion criteria and no exclusion criteria to be eligible to participate in this study.

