9.4.1. Screening Visit

The Screening visit will commence after each subject has been enrolled. Subjects who do not meet all eligibility criteria will be exited from the study.

During the Screening visit the following will be collected:

- Subject demographics
- Medical and surgical history
- Device information
- Pain medication usage

Each subject's device will be interrogated and a report session will be generated to capture the subject's initial active therapy settings.

Eligibility criteria will be evaluated to ensure subjects have a program with only 1 anode and 1 cathode with 90 μ s and 1000 Hz and the group that contains the program is used \geq 50%. Any additional programs and groups within each subject's device will be removed during this visit.

Each subject's device will be set to the program with only 1 anode and 1 cathode with 90 μ s and 1000 Hz, being used upon entry into the study, for a Baseline period lasting at least 2 weeks.

A report session will be generated to capture the subject's final active therapy settings.

Subjects will be provided with a multi-day diary and asked to record their VAS pain scores for the last 7 days of the Baseline period. A telephone call will be placed to the subjects one week before they return to the clinic to remind them to begin completing the diary. Subjects should bring their completed diary with them to the Baseline visit.

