11.3. Recording of Adverse Events

Adverse Event (AE) information will be collected from the time the subject has been enrolled until they are discontinued from the study. AE information will be reported to Medtronic on an adverse event eCRF, one for each Adverse Event.

Only those AEs which are related to the following will be collected:

- The implanted SCS system and accessories
- Spinal cord stimulation therapy

It is the responsibility of the investigator to identify the occurrence of adverse events and device deficiencies and to ensure all required information is accurately documented on the eCRF. See the eCRFs for the information to be reported for each adverse event.

Documented pre-existing conditions are not considered adverse events unless the severity of the condition has worsened and is related to the implanted SCS system, accessories, or therapy.

For adverse events that require immediate reporting, initial reporting may be done by phone, fax, or e-mail, or on the eCRF by completing as much information as is available. The adverse event eCRF must be completed as soon as possible.

In case the investigator requires information from the sponsor in an emergency, the investigator can contact the Medtronic study team using the contact details provided in Section 11.6.

The clinical course of each adverse event must be followed until the adverse event is resolved or the subject is in a stable condition. "Ongoing" adverse events must be assessed at each study visit. The adverse event eCRF should to be updated when there is a change to the information provided on the form (e.g. change in intervention, outcome, relatedness, etc.).

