13.1.1. Sample Size Justification

An estimated 60 subjects will be enrolled in order for at least 40 subjects to proceed beyond the Baseline visit. A sample size of 40 subjects is reasonable to characterize the distribution of the minimum amplitude as a percentage of perception threshold that maintains SCS therapy satisfaction, as well as to provide data for consideration of future studies.

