7.10. Safety Evaluation

The safety objective is to characterize therapy and device related adverse events and device deficiencies.

Adverse events and device deficiencies will be coded and summarized using the most recent version of Medical Dictionary for Regulatory Affairs (MedDRA).

The adverse events will also be categorized by relationship to study device and/or therapy. Adverse events will be presented in summary tables displaying the number of serious events, the number of events, and the number and percentage of subjects with one or more events. A summary of all device or therapy related adverse events and of any deaths will also be provided. A detailed narrative of each serious device or therapy related adverse event will be provided.

Device deficiencies will be presented in summary tables displaying the number of deficiencies, and the number and percentage of subjects with deficiencies.

8. Validation Requirements

Statistical programming code that affects the result of the main analysis for the primary objective shall be validated using Level I validation, which is defined as the peer reviewer independently programs output and then compares the output with that generated by the original Statistical Programmer.

Statistical programming code that affects the result of the main analysis for the secondary object shall be validated using Level II validation, which is defined as the peer reviewer reviews the code; where appropriate, performs manual calculations or simple programming checks to verify the output.

In addition, the main statistical analyses that are planned for publication and have not been previously validated should be validated with at least Level II validation.

9. References

i. Hakkinen A, Kautiainen H, Jarvenpaa S, Arkela-Kautiainen M, Ylinen J. Changes in the total Oswestry Index and its ten items in females and males pre- and post-surgery for lumbar disc herniation: a 1-year follow-up. *Eur Spine J.* Mar 2007;16(3):347-352.

ii. Fairbank JC, Pynsent PB. The Oswestry Disability Index. *Spine (Phila Pa 1976).* Nov 15 2000; 25(22):2940-2952; discussion 2952.

iii. The EuroQol Group (1990). EuroQol-a new facility for the measurement of health-related quality of life. *Health Policy* 16(3):199-208.

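### Adverse-event percentages are planned only on all enrolled subjects, with no summary for those who were titrated or by amplitude in effect at onset

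*SAP*

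**What the plan says.** The safety set carries no treatment condition: "All subjects will be included in the safety analysis set" (SAP 7.1.3). The same section defines a narrower set: "Treated analysis set will include subjects who proceed beyond the baseline visit and receive at least one programmed amplitude setting". The primary and secondary objectives use that narrower set (SAP 7.9.1.4 and 7.9.2.4).

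Protocol 8.2 fixes when a person becomes a subject: "Subjects are considered enrolled at the time the study-specific Informed Consent Form (ICF) is signed". Eligibility is checked later, at Screening and again at Baseline, and Baseline failures leave as screen failures (Protocol 9.4.2). The planned numbers are in Protocol 13.1.1: "An estimated 60 subjects will be enrolled in order for at least 40 subjects to proceed beyond the Baseline visit".

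On collection, Protocol 11.3 says "Adverse Event (AE) information will be collected from the time the subject has been enrolled until they are discontinued from the study", limited to events related to the implanted system and accessories or to the stimulation therapy. Subjects who pass Screening have their other programs removed and run on their own high-dose program "for a Baseline period lasting at least 2 weeks" (Protocol 9.4.1). The four study amplitudes follow, about two weeks each (Protocol 6.1).

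For AEs, SAP 7.10 plans counts of serious events, counts of events, and "the number and percentage of subjects with one or more events", categorised by relationship to device or therapy, with narratives for serious related events. For deficiencies it plans counts and the number and percentage of subjects. The readable text has no breakdown by analysis set, study period or amplitude.

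**The concern.** What the study does to its subjects is lower the amplitude in steps. Protocol 10.1.1.5 names the particular risk: below some level the therapy may stop working and pain may increase. Someone who exits at Screening or Baseline cannot meet that risk but still enters the denominator.

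Three things follow.

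- The percentage combines titrated subjects with people who were never titrated.
- It combines time on the subject's own setting with time under titration.
- A pooled total cannot show whether events gather at the lower amplitudes, although the study's purpose is to describe effects by amplitude.

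SAP 7.6 limits the demographic summary to Baseline-eligible subjects, so the population behind the safety percentages is also not the one the report describes. Without a data monitoring committee or clinical events committee (Protocol 12), later readers will depend largely on these tables.

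**Working it through.** The plan gives no expected AE rate, so there is no stated safety figure to reproduce. The event counts and risks below are assumptions.

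**Inputs from the documents**
- Enrolled, E = 60 (an estimate). Treated, T = 40 (a minimum). Protocol 13.1.1, SAP 6.
- Not treated: 60 − 40 = 20, or 20/60 = 33.3% of enrolled.
- Treated follow-up: about 2 weeks of Baseline period + 4 × 2 weeks of titration = 10 weeks.
- Non-treated follow-up: about 0 weeks if exited at Screening; 2 to 3 weeks if exited at Baseline (the Baseline target in Protocol 9.4.6, Table 5, is two weeks plus 7 days).

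**Person-time.** Titration: 40 × 8 = 320 person-weeks. Pre-titration time in treated subjects: 40 × 2 = 80. Non-treated: 20 × (0 to 3) = 0 to 60. The non-treated are a third of the people but a small share of the time at risk.

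**Upper limit.** With no events among the other 20:

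| Subjects with an event (assumed) | Of 40 treated | Of 60 enrolled |
|---|---|---|
| 4 | 10.0% | 6.7% |
| 8 | 20.0% | 13.3% |
| 12 | 30.0% | 20.0% |

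The relative reduction is 1 − 40/60 = 33.3% in each row.

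**Allowing events in the non-treated.** Let r be their risk relative to a treated subject. Relative reduction = 1 − [T + (E − T)r]/E = (1 − T/E)(1 − r). With T/E = 40/60:

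| r | 0 | 0.1 | 0.2 | 0.3 | 0.5 | 1 |
|---|---|---|---|---|---|---|
| Reduction | 33% | 30% | 27% | 23% | 17% | 0% |

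**Constant hazard.** If p is the treated risk over 10 weeks, the hazard is −ln(1 − p)/10, and a subject followed for w weeks has risk q = 1 − (1 − p)^(w/10). For p = 20%:
- w = 2: q = 4.4%; all-enrolled percentage (40 × 0.20 + 20 × 0.0436)/60 = 14.8%; reduction 26%.
- w = 3: q = 6.5%; all-enrolled percentage 15.5%; reduction 23%.

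Over p = 5% to 30%, the reduction is 26% to 27% at w = 2 and 22% to 23% at w = 3. It approaches 33% if most exits occur at the Screening visit itself.

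**If more than 40 of 60 are treated,** the upper limit falls: 45 gives 1 − 45/60 = 25%, 50 gives 17%, 55 gives 8%.

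**Direction after the change.** The treated-set table alters the numerator as well, because pre-titration events are moved out. If 3 of 8 subjects had only pre-titration events, the new figure is 5/40 = 12.5%, below 8/60 = 13.3%.

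**The case against.** The best defence is that an all-enrolled set suits the stated objective, which covers device- and therapy-related events and not titration alone. Every enrolled subject already has the device and the therapy. The set matches the collection window, and it retains events that follow the study's own reprogramming at Screening. That stands, and it is why the all-enrolled summary should be kept.

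The named risk is also partly visible elsewhere. Satisfaction and pain scores are summarised at each follow-up visit, and so by amplitude (SAP 7.9.1.3 and 7.9.2.3), and reasons for discontinuation are summarised (SAP 7.1.1). That also stands, but neither places AEs or device deficiencies against amplitude.

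A by-amplitude table will be hard to interpret. The order 80-60-40-20 is fixed (SAP 7.7), so amplitude and elapsed time cannot be separated. With about 40 subjects and only related events collected, cells will probably be sparse. This limits the table to description but does not remove the need to separate titration time from earlier time.

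A reader might infer that AE percentages will be cut by a full third. The documents do not support that: it needs exactly 40 treated of 60 and no events in the other 20, whereas 40 is a minimum and the others are implanted, stimulated and under AE collection from consent. A reader might also infer that the change must make the percentages look worse; the 5/40 example shows that it need not.

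**Conclusion.** The point holds as a reporting gap. The safety set, read as all enrolled, includes up to about 20 subjects on the planned numbers who never receive a study amplitude, and no readable summary separates them or the pre-titration period. The percentage of subjects with an event can understate the rate in titrated subjects by up to one third. Under a constant hazard with 2 to 3 weeks at risk, the figure is about 22% to 27%; it is at most 25%, 17% or 8% if 45, 50 or 55 of 60 are treated. Event counts do not change.

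The size rests on the planned 60 and 40 and on assumed risks, since the documents give no AE rate. The absence of an amplitude breakdown does not depend on those assumptions. It can be asserted only for the readable planned summaries: the Reports section (Protocol 13.1.4) and the additional objectives are redacted, and the AE case report form is not shown. Nothing here shows that the data could not be assigned to an amplitude.

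**What to change.** In SAP 7.1.3, state that the safety set means all enrolled subjects, and keep the SAP 7.10 summary on it. In SAP 7.10, add:

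- AE and device-deficiency tables on the treated analysis set, for events with onset after the first 80% programming, by amplitude in effect at onset, with the number of subjects exposed at each amplitude as the denominator;
- a separate summary, on all enrolled, of events between Screening and Baseline.

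Label the amplitude table as descriptive, and note that amplitude is confounded with time in the fixed sequence.

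The cost is SAP wording and one extra table with probably sparse cells. The treated set is already defined, AEs and deficiencies are recorded at every visit (Protocol Table 2), and programming reports are generated at each programming visit. The change assumes that the AE and device-event forms capture onset date, which should be confirmed. Percentages may move in either direction once pre-titration events are separated. Study conduct does not change.
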